### 3.3.2 Infusion interruption/dose modification due to CNS events

In case of CNS-related adverse events, dexamethasone should be administered at a dose of at least 24 mg/day for subjects  $\geq$  45 Kg (or 0.2-0.4 mg/kg/day divided 3-4 times per day not to exceed 24 mg/day for subjects  $<$  45 Kg). The dexamethasone dose will then be reduced step-wise over 4 days.

In case of CTCAE grade 3 or higher CNS-related adverse events, blinatumomab will be stopped immediately and a physical exam, vital signs and safety laboratory tests will be performed. Additional measures can be taken upon discretion of the investigator, depending on the nature of the adverse event. Diagnostic measures to exclude potential infectious causes should be conducted after CNS events  $\geq$  CTCAE grade 3; an assessment of cerebrospinal fluid should be performed for cytology, cell count, B- and T-cell measurement (flow cytometry at local lab), and viral studies (HSV 1/2, HSV6, JC virus and adenovirus), and magnetic resonance imaging (MRI).

Patients, who had experienced a Grade 3 CNS AE or SAE leading to treatment interruption, should have a treatment free interval of two weeks, even if the event has resolved to Grade 1 earlier. These patients will have to undergo MRI before treatment is resumed. Infusion should be re-started in the hospital, under supervision of the investigator and the patient should remain hospitalized for at least two days.

Following dexamethasone premedication, a new treatment cycle will start with a dose of 9  $\mu$ g/day if  $\geq$  45 Kg (or 5  $\mu$ g/m^2/day if  $<$  45 Kg). Blinatumomab will be escalated to 28 mcg/day if  $\geq$  45 Kg (or 15  $\mu$ g/m^2/day if  $<$  45 Kg) after 7 days if the toxicity does not recur. If the toxicity occurs at 9 mcg/day if  $\geq$  45 Kg (or 5  $\mu$ g/m^2/day if  $<$  45 Kg), or if the toxicity takes more than 7 days to resolve, blinatumomab therapy will be stopped permanently.

If the CNS event was a seizure (CTCAE grade 2 or above), appropriate prophylactic anticonvulsant treatment will be administered during the next treatment cycle.

A grade 3 CNS event leading to treatment interruption at the dose of 9 µg/day if  $\geq$  45 Kg (or 5 µg/m^2/day if  $<$  45 Kg) or a CNS event needing more than 1 week to resolve to grade  $\leq$  1 will result in permanent treatment discontinuation.

In case of CNS-related events CTCAE Grade 4 or in case of occurrence of more than one seizure the infusion of blinatumomab will have to be stopped immediately and treatment will be permanently discontinued. For patients who discontinue treatment because of a CNS event  $\geq$  Grade 3 an MRI is recommended. For patients in the additional evaluation cohort, an MRI is required after CNS event grade 3 or higher, regardless of continuation of treatment with blinatumomab.

**Table 1.** Dexamethasone premedication

Treatment phase	Target patient	Dexamethasone dose	
		Patient Weight	
		$\geq 45$ Kg	$< 45$ Kg
Pre-dose dexamethasone before each blinatumomab treatment	All patients (before each cycle and dose increase)	20 mg IV within 1 hour before start of treatment in each treatment cycle, and within 1 hour before dose increase	5 mg/m  IV within 1 hour before start of treatment in each treatment cycle, and within 1 hour before dose increase
Infusion interruption/dose modification due to adverse event	Patients who interrupt treatment $>$ 4 hours	Dexamethasone 20 mg IV within 1 hour before re-start of treatment	5 mg/m  IV within 1 hour before re-start of treatment
In case of signs of cytokine release (CRS)	Patients with signs of CRS	Dexamethasone orally or IV at a dose maximum 3 x 8 mg/day for up to 3 days. The dose should then be reduced step-wise over 4 days	Dexamethasone orally or IV at a dose 0.2-0.4 mg/kg/day divided 3-4 times per day not to exceed 24 mg/day for up to 3 days. The dose should then be reduced step-wise over 4 days
Infusion interruption/dose modification due to CNS events	Patients with CNS-related AE	Dexamethasone should be administered at a dose of at least 24 mg/day. Dexamethasone will then be reduced step-wise over 4 days.	Dexamethasone should be administered at a dose of 0.2-0.4 mg/kg/day divided 3-4 times per day not to exceed 24 mg/day. Dexamethasone will then be reduced step-wise over 4 days.

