### 3.3. Dose modifications (interruptions, withholdings, and criteria for restarting treatment) (Tables 1 and 2).

#### 3.3.1 Infusion interruption/dose modification due to adverse events

Common Terminology Criteria for Adverse Events (CTCAE) grade 4 adverse events at least possibly related to blinatumomab will require permanent

discontinuation of blinatumomab. For CTCAE grade 4 adverse events that are numerically defined laboratory parameters, independent investigator assessment should be used to determine the risk: benefit for each individual patient to continue or discontinue blinatumomab treatment.

For CTCAE grade 3, cytokine release syndrome, and CTCAE grade 3 DIC/coagulopathy, treatment with blinatumomab will be interrupted until the event resolves to at least grade 1. Blinatumomab can then be restarted at the lowest starting dose (9 µg/day if  $\geq$  45 Kg or 5 µg/m^2/day if  $<$  45 Kg). If the AE lasts for  $\geq$  2 weeks, then blinatumomab will be permanently discontinued.

For all other CTCAE grade 3 events and clinically significant laboratory value changes, investigator assessment should be used to determine the risk: benefit to continue blinatumomab therapy with or without dose reduction or discontinue therapy.

Patients who have been dose reduced will have an option to receive the higher dose level once the AE has resolved to grade 1 or less for at least 7 days. Re-start of the infusion should be performed in the hospital. Before blinatumomab is restarted, premedication with dexamethasone 20 mg if  $\geq$  45 Kg (or 5 mg/m^2 if  $<$  45 Kg) IV is required. The patient should be observed overnight for possible side effects after the restart in the hospital.

In addition to the events described above, the dose may be temporarily or permanently reduced to 9 µg/day if  $\geq$  45 Kg (or 5 µg/m^2/day if  $<$  45 Kg) if, by investigator's judgment, it is necessary for safety reasons. After at least 7 days of dosing at 9 µg/day if  $\geq$  45 Kg (or 5 µg/m^2/day if  $<$  45 Kg), the dose may be increased to 28 µg/day if  $\geq$  45 Kg (or 15 µg/m^2/day if  $<$  45 Kg) or treatment may be continued at the dose of 9 µg/day after consultation with the investigator.

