**Table 2. Management of Toxicity and Blinatumomab Dosage Adjustments**

Toxicity	Grade	Action	
		Patient Weight	
		≥ 45 Kg	< 45 Kg
Cytokine Release Syndrome (CRS)	Grade 3	Withhold blinatumomab until resolved, then restart blinatumomab at 9 mcg/day. Escalate to 28 mcg/day after 7 days if the toxicity does not recur.	Withhold blinatumomab until resolved, then restart blinatumomab at 5 $\mu\text{g}/\text{m}^2/\text{day}$ . Escalate to 15 $\mu\text{g}/\text{m}^2/\text{day}$ after 7 days if the toxicity does not recur.
	Grade 4	Discontinue blinatumomab permanently	
Neurological Toxicity	Seizure	Discontinue blinatumomab permanently if more than one seizure occurs	
	Grade 3	Withhold blinatumomab until no more than Grade 1 (mild) and for at least 3 days, then restart blinatumomab at 9 mcg/day. Escalate to 28 mcg/day after 7 days if the toxicity does not recur. If the toxicity occurred at 9 mcg/day, or if the toxicity takes more than 7 days to resolve, discontinue blinatumomab permanently.	Withhold blinatumomab until no more than Grade 1 (mild) and for at least 3 days, then restart blinatumomab at 5 $\mu\text{g}/\text{m}^2/\text{day}$ . Escalate to 15 $\mu\text{g}/\text{m}^2/\text{day}$ after 7 days if the toxicity does not recur. If the toxicity occurred at 5 $\mu\text{g}/\text{m}^2/\text{day}$ , or if the toxicity takes more than 7 days to resolve, discontinue blinatumomab permanently.
	Grade 4	Discontinue blinatumomab permanently	
Other Clinically Relevant Adverse Reactions	Grade 3	Withhold blinatumomab until no more than Grade 1 (mild), then restart blinatumomab at 9 mcg/day. Escalate to 28 mcg/day after 7 days if the toxicity does not recur. If the toxicity takes more than 14 days to resolve, discontinue blinatumomab permanently.	Withhold blinatumomab until no more than Grade 1 (mild), then restart blinatumomab at 5 $\mu\text{g}/\text{m}^2/\text{day}$ . Escalate to 15 $\mu\text{g}/\text{m}^2/\text{day}$ after 7 days if the toxicity does not recur. If the toxicity takes more than 14 days to resolve, discontinue blinatumomab permanently
	Grade 4	Discontinue blinatumomab permanently	

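### After a grade 3 CNS event, Section 3.3.2 calls for two weeks off blinatumomab, but the Table 2 row directs restart as early as day 3, and no text says which rule governs

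*Combined protocol and SAP*

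**What the plan says.** Section 3.3.2 covers CNS events. A patient with a grade 3 CNS event that interrupted treatment "should have a treatment free interval of two weeks, even if the event has resolved to Grade 1 earlier". It adds conditions for resuming. On imaging: "These patients will have to undergo MRI before treatment is resumed". The restart takes place in hospital under the investigator's supervision, and "the patient should remain hospitalized for at least two days". A new cycle then begins at the low dose.

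Table 2, grade 3 neurological row, 45 kg or more: "Withhold blinatumomab until no more than Grade 1 (mild) and for at least 3 days, then restart blinatumomab at 9 mcg/day". The column for patients under 45 kg has the same hold: "Withhold blinatumomab until no more than Grade 1 (mild) and for at least 3 days, then restart blinatumomab at 5" µg/m²/day. Neither column mentions two weeks, the MRI, the hospital stay or a new cycle.

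The heading of Section 3.3 reads "Dose modifications (interruptions, withholdings, and criteria for restarting treatment) (Tables 1 and 2"), so the table is part of the restart rules. No sentence gives the text or the table precedence.

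Two further provisions bear on the choice. Section 3.3.1 permanently discontinues treatment when an interruption for a blinatumomab-related adverse event exceeds two weeks, and allows up to 5 more days for logistical difficulties. Section 7.4 makes the same interruption a reason for removal from the study, without stating that allowance.

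**The concern.** Two restart rules for the same event give different days. Section 3.3.2 says early resolution is not a reason to resume. The table makes resolution plus a 3-day minimum enough. Staff who work from the table row alone could re-expose a patient after serious neurotoxicity days before Section 3.3.2 would allow it, and the row would not prompt them to obtain the MRI first. Two patients with the same event could be handled differently, in a trial that names toxicity attributable to blinatumomab among its feasibility parameters (Sections 1.1 and 8.2).

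The choice of rule also decides how close a patient comes to losing the drug. A two-week hold uses all the time that Sections 3.3.1 and 7.4 permit for a related event. A table-length hold does not.

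**Working it through.** The plan gives no figure to reproduce, so the check sets the rules side by side and counts days.

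**Inputs**
- Section 3.3.2: 14 days off drug, whatever the resolution day.
- Table 2, both weight columns: hold until grade 1 or less and for at least 3 days, then restart.
- Section 3.3.2 and Table 2 agree that resolution taking more than 7 days means a permanent stop.
- Section 3.3.1: an interruption of 7 days or less continues the same cycle, and a longer one starts a new cycle.
- Sections 3.3.1 and 7.4: the limit is passed when a related interruption exceeds 14 days. Section 3.3.1 alone adds up to 5 days for logistics.

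**Set-up.** Day 0 is the day the drug is stopped, and r is the day the event reaches grade 1 or less. Patients eligible to restart have r = 0 to 7. Table 2 does not say where its 3 days start, so both readings are shown.

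| Rule | Restart day | Range for r = 0 to 7 | Days earlier than day 14 |
|---|---|---|---|
| Section 3.3.2 | 14 | 14 | – |
| Table 2, 3 days counted from stopping | max(r, 3) | 3 to 7 | 14 − 7 = 7 to 14 − 3 = 11 |
| Table 2, 3 days counted from grade 1 or less | r + 3 | 3 to 10 | 14 − 10 = 4 to 14 − 3 = 11 |

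Example with r = 3: Table 2 gives day 3 on the first reading (11 days early) or 3 + 3 = day 6 on the second (8 days early). On either reading the table's restart day falls before day 14 for every eligible patient.

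**Cycle handling.** A 14-day hold exceeds 7 days, so Sections 3.3.1 and 3.3.2 both start a new cycle. A Table 2 hold is 7 days or less for every r on the first reading and for r = 0 to 4 on the second (4 + 3 = 7). Section 3.3.1 would then continue the same cycle. For r = 5 to 7 on the second reading, the hold is 8 to 10 days and a new cycle starts. The cycle difference therefore follows from the hold time.

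**Margin to the two-week limit.** Under Section 3.3.2 it is 14 − 14 = 0 days. Under Table 2 it is 14 − 7 = 7 to 11 days on the first reading, or 14 − 10 = 4 to 11 days on the second. With the logistical allowance, Section 3.3.1 tolerates up to 14 + 5 = 19 days. Section 7.4 as written does not, so a restart on days 15 to 19 could be permitted by one section and lead to removal under the other.

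**Conditions missing from the row.** These are omissions, not contradictions. MRI also appears in the Section 3.3.2 work-up after any CNS event of grade 3 or higher ("and viral studies (HSV 1/2, HSV6, JC virus and adenovirus), and magnetic resonance imaging (MRI"). Section 3.3.1 already says "Re-start of the infusion should be performed in the hospital", with overnight observation, and Section 3.1.2 asks for overnight observation after any interruption longer than 4 hours. What Section 3.3.2 adds at restart is the MRI as a condition of resuming, the investigator's supervision, and a stay of at least two days.

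**The case against.** The strongest reply is that the texts can be reconciled. The table's 3 days is a floor, so a 14-day hold complies with both. Section 3.3.2 is the dedicated CNS section and deals with early resolution expressly, so it is natural to let it govern. A reader might infer from the mismatch that the two rules cannot both be obeyed, and the documents do not support that. What remains is that the row directs restart once its conditions are met, has no footnote pointing to two weeks, and is cited in the Section 3.3 heading as part of the rules. Someone who reads both still has to guess.

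Day 3 is also an extreme case. Section 3.3.2 calls for dexamethasone with a step-wise reduction over 4 days, plus cerebrospinal fluid, viral and MRI work-up, so a day-3 restart would come before a 4-day taper could finish. Nothing forbids it, but restarts in practice may fall later in the range. A summary table may also leave out work-up steps, so the missing conditions carry little weight on their own. Section 2.5 describes life-threatening neurologic events as uncommon and generally reversible. That limits how often the problem would arise, but does not say which rule applies.

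A reader might also infer that the two-week interval itself forces discontinuation. It does not: exactly 14 days does not exceed two weeks. The difficulty is that there is no slack.

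**Conclusion.** The inconsistency is real and should be corrected. For every patient who may restart after a grade 3 CNS event, Table 2 allows restart 7 to 11 days earlier than Section 3.3.2 if its 3 days run from stopping the drug, or 4 to 11 days earlier if they run from reaching grade 1. The Section 3.3.2 hold also leaves no margin to the two-week limits in Sections 3.3.1 and 7.4, while a Table 2 hold stays at least 4 days clear.

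This assumes that the table's neurological row covers CNS events (no other row names them), that the drug is stopped at once as Section 3.3.2 requires, and that both the two weeks and the resolution time count from that day. The zero margin applies to events related to blinatumomab.

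Two wider conclusions are not supported. A reader might infer that the trial's toxicity monitoring is compromised. Section 8.3.5 counts severe acute GVHD, secondary graft failure and early non-relapse mortality, so Tables 5 and 6 do not depend on the hold time. A reader might also infer that the documents show which hold was intended, or how many patients would be affected. They show neither, and they give no rate of grade 3 CNS events.

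**What to change.** State one rule in both places, in a single amendment.

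- **Default, the more protective rule.** Amend the grade 3 neurological row of Table 2, in both weight columns, to match Section 3.3.2: two weeks off drug, MRI before resuming, in-hospital restart under the investigator's supervision with a stay of at least two days, and a new cycle at the low dose. In the same amendment, state in Sections 3.3.1 and 7.4 that the mandated two-week CNS interval plus the 5-day logistical allowance triggers neither discontinuation nor removal. Without that statement, the amended row would still sit on the limit.
- **If the clinical team intends the 3-day rule.** Delete the two-week sentence from Section 3.3.2, keep the MRI, and state whether the 3 days run from stopping the drug or from reaching grade 1, and whether the same cycle continues.

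The cost is a wording amendment. It adds no patients, and under the default it adds no procedure beyond what Section 3.3.2 already asks for. No statistical quantity changes.

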If the interruption after an adverse event is no longer than 7 days, the same cycle will be continued. The infusion duration, before and after an interruption, should total 28 days per treatment cycle. If an interruption due to an adverse event is longer than 7 days, a new cycle will start. In addition, an incomplete treatment cycle with a treatment duration of less than 2 weeks will have to be repeated (eg, if cycle 1 was interrupted on day 8 for more than 7 days, the next cycle will be denoted as cycle 1.1 and the same assessments will be performed as in cycle 1). For cycle 1.1, subjects will be started at 9 µg/day if  $\geq$  45 Kg (or 5 µg/m^2/day if  $<$  45 Kg) for the first 7 days of dosing followed by a dose step to 28 µg/day if  $\geq$  45 Kg (or 15 µg/m^2/day if  $<$  45 Kg) beginning at day 8 and continuing for the remainder of cycle 1.

An infusion interruption of more than 2 weeks due to an adverse event related to blinatumomab will lead to permanent discontinuation of treatment. In case of logistical difficulties, restart of treatment can be postponed for up to 5 additional days without resulting in permanent treatment discontinuation.

Treatment may be also interrupted or permanently discontinued at the discretion of the investigator if any clinical/laboratory adverse event is considered to be medically relevant.

In case of signs of cytokine release, dexamethasone should be administered orally or IV at a dose of at maximum 3 x 8 mg/day for subjects  $\geq$  45 Kg (or 0.2-0.4 mg/kg/day divided 3-4 times per day not to exceed 24 mg/day for subjects  $<$  45 Kg) for up to 3 days. The dose can then be reduced step-wise over 4 days.

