## 7.0 Criteria for Removal from the Study

7.1 Completion of study at 1 year.

7.2 Non-compliance by the patient with protocol requirements.

7.3 Occurrence of CTCAE grade 4 adverse event probably or definitely related to blinatumomab.

7.4 An infusion interruption of more than 2 weeks due to an adverse event related to blinatumomab.

7.5 Occurrence of a CNS-related adverse event probably or definitely related to blinatumomab, and meeting one or more of the following criteria:

- More than 1 seizure
- A CNS-related CTCAE Grade 4 adverse event
- A CNS-related adverse event leading to treatment interruption that requires more than one week to resolve to CTCAE Grade  $\leq 1$
- A CTCAE Grade 3 CNS-related adverse event leading to treatment interruption that occurred at a dose of 9 $\mu$ g/day

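### After a grade 3 CNS event, section 3.3.2 requires two weeks off drug, an MRI and a new cycle, but Table 2 permits restart from day 3, and nothing says which governs

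*Combined protocol and SAP*

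**What the plan says.** Section 3.3.2 deals with grade 3 CNS events that lead to treatment interruption. Patients "should have a treatment free interval of two weeks, even if the event has resolved to Grade 1 earlier". It adds "These patients will have to undergo MRI before treatment is resumed". On the restart itself it says "Following dexamethasone premedication, a new treatment cycle will start with a dose of" 9 µg/day, or 5 µg/m²/day below 45 kg.

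Table 2, in its grade 3 row for neurological toxicity, gives a different instruction. For patients of 45 kg or more: "Withhold blinatumomab until no more than Grade 1 (mild) and for at least 3 days, then restart blinatumomab at 9 mcg/day". For patients below 45 kg: "Withhold blinatumomab until no more than Grade 1 (mild) and for at least 3 days, then restart blinatumomab at 5" µg/m²/day. Neither column mentions a two-week interval, an MRI or a new cycle.

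The two texts agree on the rest: the low restart dose, escalation after 7 days if the toxicity does not recur, and permanent discontinuation if the event occurred at the low dose or took more than 7 days to resolve.

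Section 3.3.1 holds the general cycle rule: "If the interruption after an adverse event is no longer than 7 days, the same cycle will be continued". A longer interruption starts a new cycle.

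**The concern.** The heading of section 3.3 cites Tables 1 and 2 as part of the dose-modification rules, so both texts are operative. They address the same patients, since they share the same dose levels and the same 7-day resolution limit. Yet one excludes the early restart that the other allows, and no order of precedence is given.

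What is at stake is re-exposure after neurological toxicity. Section 2.2 says that serious neurologic toxicity was one reason for abandoning the early intermittent schedule, and section 2.5 reports seizures in both the MRD and the active-disease studies. A clinician who consults only the table could restart the drug well before 3.3.2 permits, without the imaging that 3.3.2 makes a condition of restart, and sometimes within the old cycle. Two patients with the same event could be handled differently, each in line with part of the protocol.

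**Working it through.** No figure in the plan needs reproducing, so the check is a comparison of restart dates.

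Inputs:
- Treatment-free interval in 3.3.2: 14 days.
- Minimum withholding in Table 2: 3 days, and grade 1 or below.
- Resolution limit in both texts: an event taking more than 7 days stops the drug permanently.
- Cycle rule in 3.3.1: up to 7 days, same cycle; longer, new cycle.

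Let day 0 be the day the infusion stops and r the day the event reaches grade 1 or below, with r from 0 to 7.

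- Under 3.3.2, the earliest restart is day 14 for every such r.
- Under Table 2 with the 3 days counted from stopping (reading A), it is max(3, r), which runs from day 3 to day 7.
- Under Table 2 with the 3 days counted from resolution (reading B), it is r + 3, which runs from day 3 to day 7 + 3 = 10.

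| r | 3.3.2 | Table 2, A | Gap, A | Table 2, B | Gap, B |
|---|---|---|---|---|---|
| 0 | 14 | 3 | 11 | 3 | 11 |
| 3 | 14 | 3 | 11 | 6 | 8 |
| 5 | 14 | 5 | 9 | 8 | 6 |
| 7 | 14 | 7 | 7 | 10 | 4 |

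The gap is 14 − 7 = 7 to 14 − 3 = 11 days under A, and 14 − 10 = 4 to 14 − 3 = 11 days under B. Over both readings it is 4 to 11 days. These are gaps between earliest permitted dates. Table 2 sets no latest restart day for an event that resolves in time; only the general two-week limit in 3.3.1 bounds it.

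For the cycle, a 3.3.2 restart follows an interruption of at least 14 days, which exceeds 7, so its new cycle agrees with 3.3.1. A Table 2 restart by day 7 continues the same cycle, and one from day 8 starts a new cycle. As an illustration, suppose the event comes after 14 days of infusion. A restart by day 7 leaves 28 − 14 = 14 infusion days in the cycle, whereas 3.3.2 starts a new 28-day cycle.

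**The case against.** The best defence is that the 3 days in Table 2 are a floor, so a patient held for two weeks satisfies both texts. Table 2 does not waive the MRI, and the CNS-specific text of the same section requires it. The interval is also phrased with *should*, which leaves some latitude. The first two statements are correct, but they help only a reader who already has 3.3.2 in hand. Following 3.3.2 never breaches Table 2, while following Table 2 at its minimum breaches 3.3.2. The softer verb does not reach the MRI or the new cycle, which are worded as mandatory.

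The defence is right that the different cycle is a consequence of early restart and not a separate conflict. A reader might infer that a Table 2 restart always stays in the same cycle. The documents do not support that, because a restart on day 12, say, complies with Table 2 and starts a new cycle.

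A reader might also infer that Section 7 contradicts section 3.3 at three places. The text does not carry that far:

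- **7.4** removes a patient for "An infusion interruption of more than 2 weeks due to an adverse event related to blinatumomab". The 3.3.2 minimum equals this limit (14 − 14 = 0 days of slack), but exactly two weeks is not more than two weeks. Section 3.3.1 adds: "In case of logistical difficulties, restart of treatment can be postponed for up to 5 additional days without resulting in permanent treatment discontinuation". That allows restart to day 14 + 5 = 19. Days lost to logistics are arguably not due to the adverse event, so 7.4 is ambiguous and not contradictory.
- **7.3** does not repeat the investigator's discretion that 3.3.1 gives for numerically defined grade 4 laboratory events. Section 9.3, however, does not count cytopenias and many metabolic values as adverse events, so the gap concerns mainly hepatic and renal values.
- **7.5** names only 9 µg/day in its last bullet. Dosing is unaffected, because 3.3.2 and Table 2 already stop the drug for an event at 5 µg/m²/day.

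**Conclusion.** The conflict between 3.3.2 and Table 2 is real and should be corrected. For a grade 3 CNS event resolving within 7 days, the earliest permitted restarts differ by 4 to 11 days. The table omits the MRI and the new cycle, and no text settles which rule applies.

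This rests on three assumptions: that the grade 3 neurological row and 3.3.2 cover the same events, as their shared rules indicate; that the general cycle rule in 3.3.1 applies to a restart made under Table 2; and that the 3 days run either from stopping or from resolution. The conflict stands on both readings of the 3 days.

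The documents give no frequency for grade 3 CNS events in this post-transplant setting, so the number of patients affected cannot be stated. A reader might infer damage to PFS, OS, NRM or the toxicity stopping rule. Nothing in the documents shows it. The point concerns the safety and consistency of re-exposure. The Section 7 items are editorial.

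**What to change.** Change the grade 3 neurological row of Table 2, in both weight columns, to: *withhold until grade 1 or less and for two weeks; MRI before restart; then a new cycle at 9 mcg/day (or 5 µg/m²/day if < 45 kg)*. Keep the existing escalation and permanent-stop rules. This satisfies both texts. If the clinical team deliberately prefers the 3-day rule, it should appear in both places, stating when the 3 days start, whether an MRI is needed, and whether the cycle continues.

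Editorial notes for the same amendment:
- 7.5, last bullet: add the 5 µg/m²/day dose for patients below 45 kg.
- 7.4: clarify that the 5-day logistics allowance of 3.3.1 applies.
- 7.3: cross-refer to the laboratory exception in 3.3.1.

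The cost is protocol wording only: one table row and three short phrases. Sample size, stopping boundaries and data collection do not change. The small clinical downside is a longer drug-free interval than Table 2 alone would allow.
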